## **2. Study purpose**

2.1 Main Objectives: Whether radical DA resection is associated with improvement in 5-year overall survival

2.2 Secondary objectives: Adjuvant therapy, pancreatic invasion, and advanced tumor stage were identified as significant predictors of overall survival

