Statistic analysis	
Statistical analysis
 
Rigorous statistical methods were used to analyze the collected data. Survival outcomes, including OS and DFS, were calculated from the date of diagnosis until the date of death or last follow-up, and from the date of diagnosis until the date of disease recurrence or last follow-up of DFS. Kaplan-Meier survival curves were generated to illustrate survival trends over time, and log-rank tests were used to compare the distribution of survival among different patient subgroups. Cox proportional hazard models were used to identify independent prognostic factors affecting survival. Variables considered in the model included demographic factors (age, sex), clinical features (BMI, jaundice, bleeding, anemia), preoperative laboratory values, treatment details (radical resection, adjuvant therapy), and pathological findings (AJCC stage, tumor differentiation and lymph node involvement rate). Hazard ratios (HRs) and 95% confidence intervals (CI) were calculated to estimate the strength of the association between each variable and survival outcomes.

Follow-up visit	The patients included in this study were from a hospital cohort that included cases diagnosed and treated in the Department of General Surgery at Nanfang Hospital of Southern Medical University. Inclusion criteria were histologically confirmed non-ampulla DA, including all stages of disease at diagnosis. Patients were excluded if they had ampulla cancer or other forms of gastrointestinal cancer, had incomplete medical records, or lost follow-up shortly after diagnosis.
Statistical approach	Statistical methods SPSS 25.0 and Prism 8.0.1 software were used for all statistical analyses.
Expected progress	Expected progress: From April 2024 to May 2024, data collection, sorting and analysis will be completed. From May 2024 to June 2024, monograph writing, submission and conclusion will be completed

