## **4. Study design**

This retrospective analysis was designed to clarify long-term survival outcomes in patients diagnosed with non-ampulla DA. The study spans a 15-year period, from 2009 to 2023, capturing a comprehensive dataset that reflects advancements in diagnostic and treatment strategies over time. This cohort of 400 patients was carefully selected to provide a robust data set for analyzing survival outcomes and identifying prognostic factors affecting overall survival (OS) and disease-free survival (DFS).

No randomized or any protocol-driven treatment will be administered or provided to the subjects during the study. If clinically applicable, treatment decisions and treatment options are made at the discretion of the treating physician.

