## **5. Study population**

The patients included in this study were diagnosed and treated in the Department of General Surgery of Nanfang Hospital, Southern Medical University. Inclusion criteria are histologically confirmed non-ampulla DA includes all stages of disease at diagnosis.

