## 5.2 Inclusion criteria:

- (1) At least 18 years of age;
- (2) Voluntarily sign informed consent;
- (3) Non-ampulla DA patients were diagnosed according to the Guidelines for Clinical Diagnosis and Treatment of Gastrointestinal Tumors of the Chinese Medical Association (2022 edition), including patients at all stages of diagnosis;
- (4) Unless there are no other malignant tumors in the ampulla other than DA.

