#### 6.4 Data Collection Procedure

- (1) Record demographic data: date of birth, gender, initials;
- (2) Medical history and physical examination (including vital signs, height, weight, BMI, physical examination of all systems; HCC history Present history, etiology)
- (3) Clinical presentation (symptoms, tumor location, stage of diagnosis), treatment modalities (surgical intervention, adjuvant therapy) and survival outcome (survival time, recurrence), details of surgical procedure (resection extent, lymph node dissection);
- (4) Record laboratory test results: including preoperative laboratory values (such as CEA, CA19-9 levels) and available genetic markers Markers (KRAS mutation, dMMR/MSI-H);
- (5) Pathological findings (tumor differentiation, lymphatic vascular infiltration, perineural infiltration) were recorded.

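### The resection contrast in objective 2.1 is neither restricted nor stratified by stage at diagnosis, and the Cox list does not secure a stage term on one basis for resected and unresected patients

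*Combined protocol and SAP*

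**What the plan says.** - Section 2.1 sets the main objective: "Whether radical DA resection is associated with improvement in 5-year overall survival". It does not say what radical resection is compared with, or where non-radical and palliative resections belong.
- Section 5 takes "histologically confirmed non-ampulla DA includes all stages of disease at diagnosis", and Section 5.2(3) repeats this: "including patients at all stages of diagnosis".
- Section 4 says that "treatment decisions and treatment options are made at the discretion of the treating physician".
- The survival methods stand only in the statistical analysis row of the Summary of research scheme: Kaplan-Meier curves, log-rank tests between patient subgroups, and Cox models. The Cox list includes "treatment details (radical resection, adjuvant therapy"), "clinical features (BMI, jaundice, bleeding, anemia), preoperative laboratory values", and "pathological findings (AJCC stage, tumor differentiation and lymph node involvement rate"). Section 10 adds no survival method.
- Section 6.4(3) collects "Clinical presentation (symptoms, tumor location, stage of diagnosis), treatment modalities" and so on. Section 6.4(5) collects pathology items, but no pathological stage is among them.
- Section 5.3 excludes patients with missing diagnostic or treatment data. The plan gives no other rule for missing covariates, and no stratification, matching or propensity method.

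**The concern.** Stage drives survival and is likely to drive the choice to operate. In an all-stage cohort with physician-chosen treatment, a plain comparison by resection status mixes any effect of resection with the difference in stage between the groups. Section 1 warns of selection bias in retrospective comparisons of surgery alone with surgery plus further treatment, and aims to separate the effects of tumour characteristics and surgery. The plan states no design step that does this for its main question.

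The Cox model is the only protection, and it works only if the stage term exists and means the same thing in both groups. A covariate that needs a specimen can remove unresected patients from the fit. A stage read from pathology in one group and from imaging or endoscopy in the other leaves a bias that adjustment does not remove. The answer to the main objective is at stake.

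**Working it through.** **No figure in the plan to reproduce.** The only design number is 400 patients. No effect size, event count, stage mix, resection rate or survival rate is given, so every rate below is an assumption.

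**Step 1: 5-year OS by resection status when resection has no effect.** Let m be the share with distant metastasis at diagnosis (M1; the rest are M0), and r0 and r1 the resection rates in M0 and M1. Assume 5-year OS of 50% in M0 and 5% in M1.

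- Resected: [(1−m)·r0·0.50 + m·r1·0.05] / [(1−m)·r0 + m·r1]
- Unresected: the same, with 1−r0 and 1−r1 in place of r0 and r1

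With m = 0.25, r0 = 0.80, r1 = 0.05:

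- Resected: (0.300 + 0.000625) / (0.600 + 0.0125) = 49.1%
- Unresected: (0.075 + 0.011875) / (0.150 + 0.2375) = 22.4%
- Difference: 26.7 points, from stage alone

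Over m = 15–35%, r0 = 70–90% and r1 = 5–50%, the difference runs from 5 points (15%, 70%, 50%) to 36 points (35%, 90%, 5%).

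**Step 2: hazard ratios.** Simulated Cox models: n = 400, 500 runs per row, exponential survival with the Step 1 rates, uniform censoring from 0.3 to 15 years. The adjusted model adds an M0/M1 term known for everyone.

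| m | r0 | r1 | True HR | Unadjusted HR | Share with p<0.05, unadjusted | Adjusted HR |
|---|---|---|---|---|---|---|
| 0.15 | 0.90 | 0.20 | 1.0 | 0.50 | 99% | 0.99 |
| 0.25 | 0.80 | 0.05 | 1.0 | 0.48 | 100% | 1.01 |
| 0.25 | 0.80 | 0.20 | 1.0 | 0.55 | 100% | 1.00 |
| 0.25 | 0.80 | 0.50 | 1.0 | 0.71 | 74% | 1.00 |
| 0.35 | 0.80 | 0.05 | 1.0 | 0.42 | 100% | 0.99 |

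With a true HR of 0.5, the same rows give unadjusted HRs of 0.22 to 0.39 and adjusted HRs of 0.49 to 0.51. Adjustment works when stage is known on one basis in everyone.

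**Step 3: what the Cox list secures.** There are three cases.

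- *Every covariate is available in all patients on one basis.* Step 2 applies and measured stage confounding is removed.
- *A covariate exists only after resection.* Lymph node involvement rate is the clear case. If unresected patients have no value, a complete-case fit keeps only resected patients. Resection is then constant and its HR cannot be estimated. Excluding those patients under Section 5.3 would have the same result.
- *Stage is pathological in resected and clinical in unresected patients.* Assume 25% M1; resection in 85% of node-negative, 75% of node-positive and 5% of M1 patients; median OS 80, 30 and 12 months; 30–50% of unresected node-positive patients recorded as node-negative; and 0–20% of unresected M1 recorded as M0. With a true HR of 1.0, the stage-adjusted HR is 0.68 to 0.88. One clinical rule in both groups, restricted to recorded M0, gives 0.78 to 0.94. A repeat with 30–50% of M0 patients node-positive, and missed M1 patients placed in either nodal category, gives 0.66 to 0.90 and 0.71 to 0.94. The single rule is closer to 1.0 in every scenario, but is not free of bias.

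**The case against.** The strongest reply is that AJCC stage is already in the model, and that it is probably the stage at diagnosis. Section 6.4 collects one stage item, in 6.4(3), and no separate pathological stage. Section 1 itself counts advanced stage at diagnosis among pathological features, so the heading in the Summary is weak evidence of a post-resection stage. Section 5.3 excludes patients with missing diagnostic data, so stage may be expected for everyone. The unadjusted HRs above also do not describe the planned adjusted model.

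Most of this stands. A reader might infer that unresected patients have no stage value, and that the resection association is therefore mostly stage under another name. The documents do not support that. They never say that stage is missing in unresected patients, they do list a stage term, and they give no stage mix or resection rate. Nor do they say that metastatic patients are seldom resected.

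The reply does not settle three points. The log-rank comparison has no stage adjustment. The basis of AJCC stage is left open. Lymph node involvement rate sits in the same list as radical resection, and the exclusion of incomplete records can remove unresected patients as easily as it can guarantee their data.

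Stratifying or adjusting by stage at diagnosis in the full cohort is also a fair alternative to restriction. Restriction is preferred for the main comparison because it does not rely on the model where few metastatic patients may have been resected.

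**Conclusion.** The concern holds in this form: as written, the plan does not ensure control of confounding by stage in the comparison that answers objective 2.1. The unadjusted comparison is fully exposed. The adjusted one is sound only if stage and every other covariate are available on one basis in both groups, which the plan does not state and which is doubtful for lymph node involvement rate.

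The size rests on assumed rates. With no resection effect, stage alone gives a 5-year OS difference of 5 to 36 points and unadjusted HRs of about 0.4 to 0.7. With stage known on one basis in everyone, the HR returns to about 1.0. If the basis differs between groups, an adjusted HR of roughly 0.7 to 0.9 can arise with no effect. These are illustrations, not estimates for this cohort. The point is worth settling before the models are fitted, because it decides how the main result can be read.

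**What to change.** For objective 2.1:

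1. State the comparator, including where non-radical and palliative resections belong.
2. Make the main comparison among patients without distant metastasis at diagnosis.
3. Adjust it for stage at diagnosis from Section 6.4(3), assigned by one written rule in resected and unresected patients.
4. Leave lymph node involvement rate, pathological stage and any other specimen-dependent variable out of this model. Keep them for prognostic models within resected patients.
5. Report metastatic patients descriptively, within the all-stage cohort OS that Section 3.1 already plans.
6. Label any log-rank comparison by resection status as unadjusted.

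The cost is protocol wording and one staging rule; the item is already collected. The main comparison loses the metastatic patients: at an assumed 15–35% of 400, it keeps 340 (400 × 0.85) down to 260 (400 × 0.65), so its confidence interval widens. Some bias in favour of resection can remain, because clinical staging can miss occult nodal or metastatic disease. The report should say so.

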## **3. Study endpoint**

3.1 Primary endpoints: Median overall survival, 3 - and 5-year overall survival rates for the cohort

3.2 Secondary endpoints: overall survival with adjuvant therapy, pancreatic invasion, and advanced tumor

## **4. Study design**

This retrospective analysis was designed to clarify long-term survival outcomes in patients diagnosed with non-ampulla DA. The study spans a 15-year period, from 2009 to 2023, capturing a comprehensive dataset that reflects advancements in diagnostic and treatment strategies over time. This cohort of 400 patients was carefully selected to provide a robust data set for analyzing survival outcomes and identifying prognostic factors affecting overall survival (OS) and disease-free survival (DFS).

No randomized or any protocol-driven treatment will be administered or provided to the subjects during the study. If clinically applicable, treatment decisions and treatment options are made at the discretion of the treating physician.

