The treatment of DA faces several challenges, including the lack of established guidelines based on worldwide scientific evidence, the difficulty of early detection due to the rarity of the disease and the lack of specific screening markers, and the limited evidence supporting various treatment modalities. Surgical resection is the only possible treatment for DA. The complexity of surgery, which often includes pancreaticoduodenectomy, has evolved over the years, and advances in perioperative care and surgical techniques have helped reduce morbidity and mortality, but there has been no uniform improvement in long-term survival outcomes. Adjuvant therapy, including chemotherapy and radiotherapy, has been explored as a means of improving survival, especially in cases with adverse pathological features, such as lymph node involvement or the advanced stage of diagnosis. Despite these reasons, the efficacy of adjuvant therapy for DA remains controversial. There have been no randomized controlled trials comparing the efficacy of single surgery with perioperative adjuvant treatment for DA. All of the studies were retrospective comparisons of the outcomes of surgery alone and combined surgery, so there may be selection bias in patients. Numerous meta-analyses and systematic reviews have investigated the treatment of DA in depth, but most studies have been retrospective, single-center, and small-sample size series, especially in China. To address this knowledge gap, we conducted a hospital-based cohort study designed to investigate long-

term outcomes in patients with DA and to disaggregate the effects of tumor characteristics, surgery, and adjuvant therapy on survival outcomes.

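### Year of diagnosis is not among the listed Cox covariates and no era analysis is planned, so the resection and adjuvant hazard ratios may be confounded by calendar period, in either direction

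*Combined protocol and SAP*

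**What the plan says.** Section 4 states that "The study spans a 15-year period, from 2009 to 2023" and presents the data set as one that "reflects advancements in diagnostic and treatment strategies over time". Section 10.1 makes the same statement. Section 4 also says that "treatment decisions and treatment options are made at the discretion of the treating physician".

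The only Cox specification is in the statistical analysis row of the Summary of research scheme: "Variables considered in the model included demographic factors (age, sex), clinical features (BMI, jaundice, bleeding, anemia), preoperative laboratory values", followed by "treatment details (radical resection, adjuvant therapy), and pathological findings (AJCC stage, tumor differentiation and lymph node involvement rate". No year, period or era of diagnosis is named. Section 10, including 10.1 to 10.3, adds no covariate, stratum or sensitivity analysis for calendar time.

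The main objective (section 2.1) is "Whether radical DA resection is associated with improvement in 5-year overall survival". Adjuvant therapy is among the predictors in the secondary objective (section 2.2). Overall survival is counted from diagnosis, so the date of diagnosis must already be collected.

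**The concern.** Both treatment questions are answered by non-randomised comparisons within a cohort spread over 15 years. The protocol offers changing care as a strength of the data but does not carry it into the model. Calendar time confounds a treatment hazard ratio when two things hold together: the share of patients treated changes over time, and the hazard of death changes over time for reasons the other covariates do not capture. Perioperative care is one candidate for the second link. Section 1 says it improved, and no listed covariate measures it. At stake is how far the resection and adjuvant hazard ratios can be read as treatment associations rather than partly as differences between eras.

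**Working it through.** **The plan's own figure.** The sample size of 400 (sections 8 and 10.1) comes without a hazard ratio, power, event count or share treated, so it cannot be reproduced. The documents give no trend in survival or treatment use either, so the size of the problem can only be shown under assumptions.

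**Inputs from the documents.** Diagnosis from 2009 to 2023 (section 4), 400 patients (section 8), two-sided 0.05 (section 10.3), data collection in April to May 2024 (section 11.4.3).

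**Assumptions.** Uniform accrual, follow-up to the end of April 2024, exponential survival with a mid-period median of 2.5 years, true treatment hazard ratio 1.00. With y = years since the start of 2009, the hazard is proportional to exp[b(y/15 - 0.5)] and the treated share is p0 + (p1 - p0)y/15. No other covariates are simulated, so the trend b stands for what remains after stage and the rest. exp(b) is the hazard ratio across the full 15 years. The yearly fall is 1 - exp(b)^(1/15): 1.5% for 0.80, 2.8% for 0.65 and 4.5% for 0.50.

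**Step 1: treatment hazard ratio with year left out** (100,000 simulated patients per cell)

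| Hazard ratio over 15 years | Share constant at 40% | Share 30% to 60% | Share 20% to 80% |
|---|---|---|---|
| 1.00 | 1.00 | 1.00 | 1.00 |
| 0.80 | 1.00 | 0.98 | 0.96 |
| 0.65 | 1.00 | 0.97 | 0.93 |
| 0.50 | 1.00 | 0.95 | 0.89 |

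Simulation error per cell on the log scale is about 0.116 × √(400/100,000) = 0.007. The first row and the first data column show that neither trend alone produces bias. With a linear year term, every cell returns to 0.99-1.01.

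**Step 2: direction.** Swapping the labels treated and untreated inverts the hazard ratio. A treated share falling from 70% to 40% mirrors a rise from 30% to 60%, so with a 15-year hazard ratio of 0.50 it gives 1/0.95 = 1.05. A fall from 80% to 20% gives 1/0.89 = 1.12. The bias then runs against treatment.

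**Step 3: size at 400 patients.** The simulated standard error of the treatment log hazard ratio is 0.115-0.116. As a check, with 309 deaths and 45% treated, 1/√(309 × 0.45 × 0.55) = 0.114. The table gives the shift in standard errors and the false-positive rate over 1,000 replicates.

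| Scenario | Shift | False positives, year left out | False positives, year included |
|---|---|---|---|
| No trend, 30% to 60% | 0 | 5.7% | 5.2% |
| 0.80, 30% to 60% | 0.02/0.115 = 0.2 | 5.1% | 4.9% |
| 0.65, 30% to 60% | 0.03/0.116 = 0.3 | 5.8% | 5.5% |
| 0.50, 30% to 60% | 0.05/0.116 = 0.4 | 7.2% | 5.5% |
| 0.50, 20% to 80% | 0.11/0.116 = 1.0 | 16.5% | 6.0% |

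Monte Carlo error near 5% is √(0.05 × 0.95/1,000) = 0.7 percentage points, so the second and third rows cannot be told from 5%.

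**Step 4: comparison with a detectable effect.** The hazard ratio detectable with 80% power is exp[-(1.960 + 0.842)/√(D p(1 - p))]. For an assumed D of 200-280 deaths and p of 30-70% treated, this is 0.65-0.72. With D = 310, close to the simulated count, and p = 50%, it is 0.73.

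**Step 5: follow-up by period.** With a cut-off at the end of April 2024, 4.67/15 = 31% of patients have less than 5 years of potential follow-up. Of about 400/3 = 133 patients diagnosed in 2019-2023, only 0.33/5 = 7%, about 9, could be observed for 5 years. For 3 years the share is 2.33/5 = 47%, about 62.

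**The case against.** The case for leaving the model alone has substance. Stage, differentiation and nodal involvement are already listed, so gains that come from earlier diagnosis are at least partly absorbed. Gains that come from wider use of resection or adjuvant therapy are the effect under study, not confounding. Only a residual trend matters, and section 1 says of the field that advances have come "but there has been no uniform improvement in long-term survival outcomes". The covariate list may also be open: it says which variables were included, and it omits pancreatic invasion although section 2.2 names that as a predictor.

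What stands is that the trend must be residual, that its existence and direction are unknown, and that the likely bias is modest. What does not stand is that nothing need be done. The remark in section 1 concerns the field rather than this hospital, and a lack of uniform improvement is not a lack of improvement. Section 4 says diagnostic methods advanced too, so a given recorded stage may not mean the same in 2009 as in 2023, and adjusting for stage need not remove the trend. An open list commits nobody to include year.

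**Conclusion.** The omission is plain on the face of the documents. Its effect is conditional. If use of either treatment and residual survival both changed over 2009-2023, the resection and adjuvant hazard ratios may be confounded by era. Under assumed residual hazard falls of 1-5% per year with rising use, a true hazard ratio of 1.0 would appear as roughly 0.9 to 1.0. That is at most about one standard error at 400 patients, and the false-positive rate rises materially only when steep trends in both coincide.

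A reader might infer that calendar-time gains are in fact being credited to resection and adjuvant therapy, or that both estimates lean towards benefit. The documents do not support that. They report neither a survival trend in this cohort nor a change in treatment use, and falling use alongside improving survival would reverse the sign. Nor does the point reach the primary endpoints in section 3.1: median survival and the 3- and 5-year rates for the cohort do not depend on which covariates enter the Cox model.

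**What to change.** Add year of diagnosis to the Cox covariate list, either continuous or as the periods 2009-2013, 2014-2018 and 2019-2023, or stratify the Cox model by period. Tabulate resection use, adjuvant use and overall survival by period, so that readers can see whether either trend exists. Limit the 2019-2023 survival estimates to a shorter horizon, for example up to 3 years with numbers at risk, because few of those patients can reach 5 years by May 2024.

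This is a free improvement. It costs one or two degrees of freedom. In the scenarios run at 400 patients with a linear year term, the standard error of the treatment log hazard ratio rose by at most about 5% (0.116 to 0.122). No new data are needed.
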